The following endpoints, considered as simple binary outcomes, will be analyzed using a logistic regression analysis with a fixed effect for randomized treatment and baseline eGFR included as a covariate. The analysis will be stratified by the randomization strata. The treatment effect estimate from the model will be the contrast between sparsentan and irbesartan log odds. The treatment effect estimate, and its 95% CI will be back-transformed to provide results on the odds ratio scale, and the associated two-sided p-value will be presented as follows:

- The proportion of patients achieving a urinary protein excretion of  $<0.3$  g/day up to Week 110.
- The proportion of patients achieving a urinary protein excretion of  $<1.0$  g/day up to Week 110.
- The proportion of patients requiring systemic immunosuppressive medication during the study.
- The frequency of hospitalizations (for any reason and for reasons related to the kidney).

The proportion of patients reaching a confirmed 40% change from baseline in eGFR, ESRD, or death will be analyzed via PROC PHREG in SAS in terms of the time to the first of a confirmed 40% change from baseline in eGFR, ESRD, or death using a Cox regression model stratified for the randomization stratification factors and with a fixed effect term for randomized treatment. The hazard ratio along with its 95% CI and two-sided p-value will be provided. The data will also be displayed by randomized treatment group using Kaplan-Meier estimates of the cumulative density function.

The use of systemic immunosuppressive medication and the frequency of hospitalizations will also be analyzed in terms of the number of systemic immunosuppressive medications and the

number of hospitalizations for any reason per patient, using a Negative Binomial regression model via PROC GENMOD in SAS. The model will be stratified for the randomization stratification factors and will include a fixed effect term for randomized treatment. The analyses will be adjusted for duration of exposure to randomized treatment. Estimated event rates will be extracted from the model for each randomized treatment. The treatment effect will be presented as the ratio of event rates together with the associated 95% CI and two-sided p-value.

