#### **8.4.3. Procedure for Testing Other Secondary Endpoints Within the US and Non-US Countries**

At the time of the final (confirmatory) analysis, if all the key secondary endpoints achieve statistical significance within the US or non-US countries, the other secondary endpoints will be statistically tested at the available alpha in the order specified below:

1. The mean change from baseline in UP/C at Week 110
2. The mean change from baseline in urine protein excretion at Week 110
3. The mean change from baseline in UA/C at Week 110
4. The mean change from baseline in urine albumin excretion at Week 110
5. The proportion of patients reaching a confirmed 40% reduction in eGFR, ESRD, or death
6. The mean change from baseline in eGFR at Week 110

The multiple testing strategies for the US and for non-US countries are shown in [Figure 1](#).

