### **8.7.3. Other Continuous Endpoints**

The following exploratory endpoints will be analyzed using an MMRM as described for the primary efficacy endpoint ([Section 8.5.1](#)). Missing data will not be imputed using the MI procedure:

- The mean change from baseline in eGFR and selected proteinuria variables, based on a 24-hour urine sample (eg, urine protein excretion, urine albumin excretion, UA/C, and UP/C), up to Week 110
- Mean changes from baseline in QoL, measured via PRO at each visit
- Change from baseline for blood pressure will also be analyzed at both primary analysis and at final analysis.

The following exploratory endpoints will be analyzed using an ANCOVA analysis:

- The change from baseline in eGFR at 6 weeks post randomization (ie, the acute effect of randomized therapy)
- The change from EOT (ie, Week 110) in eGFR 4 weeks following cessation of treatment (ie, at Week 114)
- Duration of hospitalizations (for any reason and for reasons related to the kidney)

Specifically, the change from baseline or EOT or duration (as applicable) will be the dependent variable, treatment group, and randomization stratification strata as fixed effects and baseline value as covariate. The treatment effect will be the contrast between sparsentan and irbesartan LS means. The LS means, treatment effect estimate, 95% CI, and p-value will be presented.

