### **8.7.4. Other Responder Endpoints**

Responder endpoints will be summarized at both the primary and final analysis. For these responder endpoints, patients are classified as either a responder or a non-responder.

The following endpoints will be analyzed via a logistic regression model with a fixed effect for treatment and baseline eGFR (baseline urinary protein excretion for complete remission defined as urinary protein excretion <0.3 g/day, partial remission defined as urinary protein excretion <1.0 g/day) as a covariate, stratified by the randomization strata:

- The proportion of patients reaching a confirmed 40% reduction in eGFR, ESRD, or death
- The proportion of patients achieving urinary protein excretion <0.3 g/day up to Week 110

- The proportion of patients achieving urinary protein excretion  $<1.0$  g/day up to Week 110

The treatment effect estimate from the model will be the contrast between sparsentan and irbesartan log odds. The treatment effect estimate and its 95% CI will be back-transformed to provide results on the odds ratio scale, and the associated 2-sided p-value will be presented.

Reduction of eGFR requires confirmation by a value at least 4 weeks after the initial value. If the last value on randomized treatment is the initial value for reduction or eGFR  $<15$  mL/min/1.73 m^2, then the last value on randomized treatment is considered confirmed or sustained. ESRD is defined as initiation of RRT or sustained eGFR  $<15$  mL/min/1.73 m^2 during the study (confirmed after repeat assessment of at least 14 days after initial assessment).

The following endpoint will be analyzed using a generalized mixed model repeated measure analysis using PROC GLIMMIX in SAS:

- Proportion of patients with hematuria at each visit as determined by presence of blood in urinalysis
- Proportion of patients with use of systemic immunosuppressive medication during each 12-week time bucket.

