#### **8.7.4.1. Time-to-Event Analyses**

The time to occurrence of the following endpoints will be also analyzed at both the primary and final analyses:

- First confirmed 40% reduction in eGFR, ESRD, or death
- Initiation of systemic immunosuppressive medication (all and renal indication only)

Time-to-event data will be analyzed using a Cox regression model, stratified by randomization strata, via PROC PHREG in SAS. The tabulation will also include the KM estimates of the medians and corresponding 95% CIs if the medians can be estimated. The number and percent of patients censored and with events will be presented. Patients without any documentation of events will be censored at the time of analysis (if still on randomized treatment) or the time of discontinuation of randomized treatment, whichever is earlier.

For patients with an event for the first confirmed 40% reduction in eGFR, ESRD, or death endpoint, the minimum of the following event dates will be used:

- Death
  - Date of death
- ESRD
  - Date of initiation of RRT
  - Date of first occurrence of eGFR  $<15$  mL/min/1.73 m^2 (confirmed after repeat assessment of at least 14 days after initial assessment)
- Confirmed 40% reduction from baseline in eGFR
  - Date of first assessment meeting criteria

Reduction of eGFR requires confirmation by a value at least 4 weeks after the initial value. If a patient experiences more than one of these events, only the event that occurs first will be included in the analysis.

Additional sensitivity analysis may be performed at final analysis if there are sufficient events after premature treatment discontinuation during the double-blind period.

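### The kidney composite, item 5 in the SAP's alpha-controlled order, has two analyses in the SAP and no named deciding test, while the protocol specifies stratified Cox only

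*SAP*

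**What the plan says.** SAP 8.4.3 lists six other secondary endpoints for formal testing in a fixed order at the available alpha, once all key secondary endpoints are significant. Item 5 is "The proportion of patients reaching a confirmed 40% reduction in eGFR, ESRD, or death". No model is named for any item. For items 1–4 and 6 this does no harm, because SAP 8.7.3 gives them one analysis: "The following exploratory endpoints will be analyzed using an MMRM as described for the primary efficacy endpoint".

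Item 5 has two analyses in the SAP.

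- SAP 8.7.4: "The following endpoints will be analyzed via a logistic regression model with a fixed effect for treatment and baseline eGFR". The first endpoint listed under it has the same wording as item 5. A two-sided p-value is presented.
- SAP 8.7.4.1: "The time to occurrence of the following endpoints will be also analyzed at both the primary and final analyses". The composite is on that list, and the model is a stratified Cox regression.

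Protocol 12.7.4 analyses the composite only as time to first event, "using a Cox regression model stratified for the randomization stratification factors", with a two-sided p-value. Its list of logistic endpoints does not include the composite. SAP 5.4 declares consistency with Protocol Amendment 5 and does not mention a logistic analysis of the composite as a change.

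**The concern.** An item in a fixed-sequence procedure needs one p-value fixed in advance. Here two are available from the same data, and the result decides both the claim on the composite and whether item 6 (change in eGFR at Week 110) is tested.

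The two tests also do not measure the same thing. Under SAP 8.7.4 "patients are classified as either a responder or a non-responder". SAP 6.5.4 and 8.1 restrict efficacy assessments to Week 110 to those on treatment, meaning up to 3 days after the last dose. A patient who stops at Week 20 without an event therefore counts the same as one observed event-free to Week 110. If the arms stop at different rates, the logistic comparison mixes treatment effect with length of observation. The Cox model uses the observed time.

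**Working it through.** **1. The plan's own figure.** The alpha feeding this sequence reproduces. In the non-US procedure 0.01 (1-year slope) + 0.04 (final analysis) = 0.05, and the US procedure uses 0.05. The documents give no event rate, stopping rate, hazard ratio or power for the composite, so every rate below is an assumption.

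**2. The texts side by side.**

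| | Protocol 12.7.4 | SAP 8.7.4 | SAP 8.7.4.1 |
|---|---|---|---|
| Model | Stratified Cox | Logistic, stratified | Stratified Cox |
| Baseline eGFR as covariate | No | Yes | Not stated |
| Rule for unequal follow-up | Implicit in time to event | None | Censor at analysis or at stopping |
| Last on-treatment value taken as confirmed | Not stated | Yes | Not repeated |
| Labelled as deciding test | Only test given | No | No |

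**3. Bias of the logistic comparison, closed form.** Assume constant hazards, event incidence 15% by Week 110 in both arms (hazard ratio 1), stopping by Week 110 of 35% in one arm and 15% in the other, stopping unrelated to outcome, and events counted only before stopping. Let a = −ln(1 − incidence) and b = −ln(1 − stopping proportion). Then

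P(event on treatment) = a/(a + b) × [1 − exp(−(a + b))].

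- a = −ln 0.85 = 0.1625.
- 35% arm: b = −ln 0.65 = 0.4308. P = 0.1625/0.5933 × (1 − 0.85 × 0.65) = 0.2739 × 0.4475 = 0.1226.
- 15% arm: b = 0.1625. P = 0.5 × (1 − 0.85 × 0.85) = 0.5 × 0.2775 = 0.1388.
- Odds ratio = (0.1226/0.8774) / (0.1388/0.8613) = 0.87, in favour of the arm that stops more.

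With 190 per arm (380 allocated 1:1), SE(log OR) = √[1/(190 × 0.1226 × 0.8774) + 1/(190 × 0.1388 × 0.8613)] = 0.305. The shift is 0.1425/0.305 = 0.467 standard errors. Two-sided rejection at nominal 0.05 is P(Z > 1.493) + P(Z > 2.427) = 0.068 + 0.008 = about 0.075.

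**4. Simulation on the same assumptions** (190 per arm, hazard ratio 1, 6,000 trials per scenario, Monte Carlo SE about 0.003, incidence 10–25%, constant or rising hazard):

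| Stopping | Logistic type I error | Cox type I error |
|---|---|---|
| 15% v 15% | 0.047–0.051 | 0.043–0.049 |
| 25% v 15% | 0.053–0.068 | 0.043–0.052 |
| 35% v 15% | 0.064–0.136 | 0.040–0.051 |

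The constant-hazard, 15%-incidence value at 35% v 15% is 0.075, which matches step 3.

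**5. Under a true effect.** A second simulation (380 patients, about 1,500 runs per scenario, hazard ratio 0.6) had the two tests disagreeing at 0.05 in 2.7–5.1% of trials with equal 15% stopping. With 10% stopping on sparsentan and 30% on irbesartan they disagreed in 9.1–21.6%. Logistic power there was lower than Cox power: 0.145 v 0.229, 0.220 v 0.349 and 0.344 v 0.560 at control risks of 10%, 15% and 25%. The logistic test can therefore work against sparsentan as well as for it.

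**6. Event rule.** SAP 8.7.4 says of a qualifying last value that "then the last value on randomized treatment is considered confirmed or sustained". SAP 8.7.4.1 restates "Reduction of eGFR requires confirmation by a value at least 4 weeks after the initial value" and the 14-day rule for ESRD but not that clause.

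**7. Follow-up cut-off.** SAP 8.7.4.1 dates death and renal replacement therapy with no on-treatment limit but censors event-free patients at discontinuation. Take two patients who stop at Week 30. If one dies at Week 100, the literal text gives an event at Week 100, while the survivor is censored at Week 30.

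**The case against.** **The protocol is clear, and the SAP leans one way.** A reader might infer that no document says which test decides. That goes too far. The protocol names one test, and the SAP leans to logistic because item 5 repeats the logistic wording and Cox comes second as an addition. What stands is a missing label in the SAP and a difference from the protocol. The wording cannot settle it, because the protocol also calls the endpoint a proportion and analyses it by Cox.

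**The departure cannot be fully verified.** SAP 5.4 refers to Amendment 5; the protocol supplied is Amendment 6. The Amendment 6 entry in the protocol history lists no statistical change, so the difference probably existed then, but this is not proven.

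**The event definitions probably agree.** Section 8.7.4.1 is a subsection of 8.7.4, so the last-value clause ordinarily carries over. The texts do not show that the two analyses count different events, only that one sentence is missing.

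**Events after stopping may already be excluded.** Section 8.7.4.1 allows a further analysis if enough events occur after premature discontinuation, which suggests that the main Cox analysis leaves them out. The uneven cut-off in step 7 is one literal reading. If deaths and renal replacement after stopping do count in the logistic analysis, its bias is smaller than in steps 3 and 4 by an amount not calculated here.

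**Cox is not a guarantee.** Its error rate holds in step 4 because stopping was made unrelated to outcome. In a check with stopping in one arm dependent on event risk (4,000 runs, hazard ratio 1), an unstratified log-rank test rejected in 0.087–0.112 of trials at 35% v 15%, and a comparison of proportions in 0.169–0.258. Cox remains the better choice, but the on-treatment restriction itself can still mislead.

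**Conclusion.** The point holds in limited form. Item 5 lacks a named deciding test in the SAP, the SAP's natural reading differs from protocol 12.7.4, and that reading ignores unequal follow-up. The textual finding needs no assumptions.

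The size of the bias does need them. The odds ratio of 0.87 at a hazard ratio of 1 rests on 15% incidence, 35% v 15% stopping, constant hazards and on-treatment events only. The top simulated error of 0.136 needs 25% incidence, a rising hazard and that stopping gap together. These figures should not be read as a forecast that the test will be inflated. With equal stopping both tests are valid, and the only question is which one counts.

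The stakes are confined to items 5 and 6, reached only after the primary endpoint, the key secondary endpoints and four proteinuria tests have succeeded. The change should be made, but the primary and key secondary conclusions do not depend on it.

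**What to change.** (a) In SAP 8.4.3, name the protocol's stratified Cox model as the single deciding test for item 5. Label the logistic model in 8.7.4 supportive, and record the decision in 5.4.

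(b) In SAP 8.7.4.1, state that the event definition of 8.7.4 applies, and say explicitly whether the last-on-treatment-value clause carries over.

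(c) State that events and censoring use the same follow-up cut-off. Pre-specify the analysis of all events to Week 114, regardless of treatment status, as a sensitivity analysis in place of the present conditional wording, because censoring at treatment discontinuation may be informative.

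The cost is SAP wording and a little programming. No new visits are needed, since protocol 6.3.2 already encourages visits through Week 114 after study medication is stopped. The downside is in interpretation: events after stopping may dilute the effect in the sensitivity analysis, and Week 114 values are taken off study drug after standard care has resumed, so they may partly reflect withdrawal of treatment.

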The total duration of hospitalizations for any reason per patient will be further analyzed using analysis of covariance with a fixed effect term for randomized treatment and baseline eGFR included as a covariate. The analysis will be stratified by the randomization factors. The treatment effect will be the contrast between sparsentan and irbesartan LS means. The LS means, treatment effect estimate, 95% CI, and p-value will be presented.

The proportion of patients with hematuria at each visit will be analyzed using a generalized, mixed-model, repeated-measures analysis using PROC GLIMMIX in SAS. Fixed effects will be included for baseline eGFR value (30 mL/min/1.73 m^2 to <60 mL/min/1.73 m^2 and ≥60 mL/min/1.73 m^2) and urine protein excretion (≤1.75 g/day and >1.75 g/day), as well as for randomized treatment, visit, and randomized treatment-by-time interaction. Patient will be included as a random effect. A logit link function will be used with distribution set to binomial. An unstructured covariance matrix will be assumed; if convergence issues arise, a first-order, auto-regressive structure will be used. Treatment effect estimates will be extracted from the model at each visit in terms of the difference between randomized treatments in log odds, together with the associated 95% CI and two-sided p-values. Treatment effects and CIs will be back-transformed to provide results on the odds ratio scale.

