**Table 15.1-1. Double-blind Period: Schedules of Study Events from Screening Through Week 36**

Week	Screening	Randomization	Blinded Treatment Period					
	1	Day 1	Week 2	Week 4	Week 6	Week 12	Week 24	Week 36
Visit	1	2	3	4	5	6	7	8
Visit Window	28 Days Prior to Day 1	--	14 ± 5 days	± 5 days	± 5 days	± 7 days	± 14 days	± 14 days
Informed Consent	X							
Inclusion/Exclusion	X							
Medical History	X							
Demographics	X							
Full Physical Examination	X	X						
Targeted Physical Examination			X	X	X	X	X	X
Peripheral Edema Assessment a	X	X	X	X	X	X	X	X
Vital Signs b	X	X	X	X	X	X	X	X
Screening Tests c	X							
Clinical Laboratory Assessments Panel A d	X	X			X	X	X	X
Clinical Laboratory Assessments Panel B e			X	X				
Lipid Panel f	X f				X	X	X	X
NT-proBNP	X		X		X	X	X	X
Aldosterone, Renin		X			X	X	X	
Endothelin		X			X	X	X	
Biorepository Samples (blood and urine, if consented)		X				X		X
Coagulation Tests (Prothrombin Time, INR)	X				X		X	
Quantitative urinalysis (24-hour collection) g	X	X		X	X	X	X	X
Calculate eGFR h	X	X	X	X	X	X	X	X

Week	Screening	Randomization	Blinded Treatment Period					
	--	Day 1	Week 2	Week 4	Week 6	Week 12	Week 24	Week 36
Visit	1	2	3	4	5	6	7	8
Visit Window	28 Days Prior to Day 1	--	14 ± 5 days	± 5 days	± 5 days	± 7 days	± 14 days	± 14 days
PK plasma levels (sparsentan, irbesartan) i					X	X		X
Pregnancy Test j	X	X	X	X	X	X	X	X
QoL Questionnaire k		X					X	
12-lead Electrocardiogram l	X							
Dispense Urine Pregnancy Tests m					X	X	X	X
Study Medication Dispensing n		X	X	X	X	X	X	X
Study Medication Accountability			X	X	X	X	X	X
Randomization		X						
Adverse Event Assessment	-----Continuous Monitoring -----							
Concomitant Medications/Therapies	-----3 Months prior to screening followed by Continuous Monitoring -----							

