d Includes clinical chemistry (serum sodium, potassium, chloride, bicarbonate, total protein, albumin, calcium, phosphate, glucose, hemoglobin A1c, cystatin, uric acid, BUN, creatinine [including calculation of eGFR], bilirubin [total, direct, and indirect], ALT, AST, ALP, gamma glutamyltransferase, creatine kinase, amylase, and lipase); hematology (red blood cells, hemoglobin, hematocrit, MCV, MCH, MCHC, platelets, WBC, and WBC differential [neutrophils, eosinophils, basophils, lymphocytes, and monocytes, percentage and absolute]); and routine urinalysis (color, appearance, and dipstick [pH, specific gravity, protein, glucose, ketones, bilirubin, blood, urobilinogen, and leukocyte esterase]). It is strongly recommended that patients come to the study visit in a fasted state, and patients should remain fasted until their blood samples have been collected. If the patient has not been fasting, it should be documented accordingly in the eCRF.

e Includes clinical chemistry (same as footnote d but excluding phosphate, hemoglobin A1c, cystatin, and uric acid); hematology (same as footnote d but excluding WBC differential); and routine urinalysis (same as footnote d). It is strongly recommended that patients come to the study visit in a fasted state, and patients should remain fasted until their blood samples have been collected. If the patient has not been fasting, it should be documented accordingly in the eCRF.

- f Includes total cholesterol, LDL (direct), HDL (direct), and triglycerides (direct). At screening, only total cholesterol and triglycerides are required.
- g For screening, patients will be given supplies for collection of a 24-hour urine sample at Visit 1 and will return with the collected sample within the visit window. For other visits, the sample will be collected 24 hours immediately prior to the visit. Patients who forget to collect this sample the 24 hours immediately prior to the visit may collect and return it within the visit window. Protein and albumin excretion, creatinine, sodium, and urea will be measured from this sample. If the sample for the screening visit is collected within 14 days prior to Visit 2, the sample (and calculation of eGFR) for Visit 2 is not necessary.
- h Calculated using the CKD-EPI formula based on age, sex, race, and serum creatinine values from the visit.

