### 3.2.2. Exploratory Endpoints – Double-Blind Period

Exploratory endpoints are listed below:

- The rate of change in eGFR over a 58-week (approximately 1-year) period following the initiation of randomized therapy (thus, the analysis is from Day 1 to 58 weeks post randomization; eGFR total slope at 1 year)
- The change from baseline in eGFR at 6 weeks post randomization (ie, the acute effect of randomized therapy)
- The change from end of treatment (EOT, ie, Week 110) in eGFR 4 weeks following cessation of treatment (ie, at Week 114)
- Change in eGFR from baseline to 4 weeks post cessation of randomized treatment (Week 114)
- Achievement of urinary protein excretion of <0.3 g/day up to Week 110
- Achievement of urinary protein excretion of <1.0 g/day up to Week 110
- The proportion of patients with hematuria at each visit
- Changes from baseline in blood pressure at each visit
- The proportion of patients requiring systemic immunosuppressive medication during the study
- Mean changes from baseline in quality of life (QoL), measured via patient-reported outcome (PRO) at each visit
- Frequency and duration of hospitalizations (for any reason and for reasons related to the kidney)
- Trough plasma pharmacokinetic (PK) concentrations

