#### 4.4. Randomization

Randomization will be carried out using an interactive response technology (IRT) system, with central randomization following a 1:1 ratio between the 2 treatment arms, based on a permuted-block randomization method. Randomization will be stratified by the following factors:

- eGFR value at Screening (30 to <60 mL/min/1.73 m^2 and ≥60 mL/min/1.73 m^2)
- Urine protein excretion at Screening (≤1.75 g/day and >1.75 g/day)

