### **6.4. Baseline Definition**

#### **6.4.1. Double-Blind Baseline**

Double-blind baseline is defined as the last nonmissing assessment prior to and including the first administration of study medication (including unscheduled assessments) in the study. In the case where the last nonmissing assessment and the study medication start date (and time if available) coincide, that assessment will be considered baseline. Unless explicitly stated, all baseline used in this SAP will refer to the double-blind baseline.

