Specifically, the model will include treatment, time (ie, nominal visit in weeks), treatment by time interaction, and stratification strata factors as fixed effects, and patient as a random effect. A logit link function will be used with distribution set to binomial. An unstructured covariance matrix will be assumed; if convergence issues arise, a first order autoregressive structure will be used. Treatment effect estimates will be extracted from the model at each visit in terms of the difference between treatments in log odds, together with the associated 95% CI and 2-sided p-values. Treatment effects and CIs will be back transformed to provide results on the odds ratio scale.

At the primary analysis, analysis models without stratification by randomization strata or other simpler models may be used if sparsity of data causes model convergence issues.

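### The exploratory hematuria model leaves out baseline hematuria, which is scheduled for every patient, and so loses some precision that one covariate would recover

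*SAP*

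**What the plan says.** SAP 3.2.2 lists "The proportion of patients with hematuria at each visit" among the exploratory endpoints. SAP 8.7.4 defines the outcome as "Proportion of patients with hematuria at each visit as determined by presence of blood in urinalysis" and fits it with PROC GLIMMIX, where "the model will include treatment, time (ie, nominal visit in weeks), treatment by time interaction, and stratification strata factors as fixed effects" and patient is a random effect. The same sentence serves a second endpoint, use of systemic immunosuppressive medication in 12-week intervals.

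Protocol 12.7.4 describes the same kind of model. There, "Fixed effects will be included for baseline eGFR value" and for urine protein excretion, both categorized at the stratification cut-points, together with treatment, visit and their interaction. Neither document includes baseline hematuria or gives a reason for leaving it out.

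The baseline measurement is planned. Protocol Table 15.1-1 marks "Clinical Laboratory Assessments Panel A" at Screening and Day 1, and footnote d says that this panel contains "routine urinalysis (color, appearance, and dipstick [pH, specific gravity, protein, glucose, ketones, bilirubin, blood, urobilinogen, and leukocyte esterase". SAP 6.4.1 supplies the rule for choosing the value: "Double-blind baseline is defined as the last nonmissing assessment prior to and including the first administration of study medication". A Screening dipstick therefore stands in if Day 1 is missing.

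**The concern.** Hematuria status before treatment is an obvious candidate predictor of hematuria status during treatment. The stratification factors are Screening eGFR and "Urine protein excretion at Screening" (SAP 4.4), so nothing in the fixed part of the model carries hematuria directly.

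Elsewhere the SAP does adjust for the endpoint's own baseline:

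- log baseline UP/C in the primary model (8.5.1);
- baseline eGFR in the slope models (8.6.1, 8.6.2);
- the baseline value in the change-from-baseline ANCOVAs (8.7.2, 8.7.3);
- baseline urinary protein excretion in the remission models (8.7.4).

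The last is telling. Protocol 12.7.4 adjusted the remission endpoints for baseline eGFR, and SAP 8.7.4 uses the endpoint's own baseline instead. The hematuria model in the same section was not treated likewise.

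What is at stake is the width of the interval for the hematuria odds ratio at each visit, and the power of its nominal test.

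**Working it through.** **Is there a planned figure to reproduce?** Not for hematuria: the documents state no prevalence, effect size or power for it. As an anchor, the primary endpoint's power does reproduce. With 140 per arm, a log-scale SD of 0.92 and a 30% relative effect (SAP 4.3.1), the standard error is 0.92 × √(2/140) = 0.110. The standardized effect is |ln 0.7|/0.110 = 0.357/0.110 = 3.24, and power is Φ(3.24 − 1.96) = 0.90, as stated.

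**Inputs from the documents.** About 380 patients, 1:1 allocation, four strata, and a logistic model with visit, treatment by visit, strata and a patient random effect.

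**Assumed inputs, not in the documents.** Baseline hematuria prevalence of 50%, 80% or 95%; patient SD on the logit scale of 1, 2 or 3 (the larger it is, the more stable a patient's status over time); and a patient-level treatment log odds ratio of −0.8 or −1.0 (0 for the null).

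**Method.** A random-intercept logistic model with four post-baseline visits was simulated 150 times per setting and fitted by maximum likelihood, with and without one baseline-hematuria term. The last-visit treatment contrast was tested at two-sided 5%. The variance ratio is (SE with ÷ SE without)², from median standard errors.

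| Prevalence | Patient SD | Log OR | SE without | SE with | Variance ratio | Power without → with |
|---|---|---|---|---|---|---|
| 50% | 1 | −0.8 | 0.257 | 0.253 | 0.97 | 0.89 → 0.91 |
| 50% | 2 | −0.8 | 0.344 | 0.316 | 0.84 | 0.67 → 0.74 |
| 50% | 3 | −1.0 | 0.446 | 0.381 | 0.73 | 0.61 → 0.71 |
| 80% | 1 | −0.8 | 0.280 | 0.277 | 0.98 | 0.80 → 0.81 |
| 80% | 2 | −0.8 | 0.377 | 0.354 | 0.88 | 0.60 → 0.62 |
| 80% | 3 | −1.0 | 0.497 | 0.436 | 0.77 | 0.60 → 0.65 |
| 95% | 2 | −1.0 | 0.556 | 0.543 | 0.95 | 0.41 → 0.44 |

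For example, (0.381/0.446)² = 0.73, a 27% reduction.

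**Type I error.** Under the null (60% prevalence, SD 2), rejection was 0.053 without and 0.067 with the term. The Monte Carlo standard error is √(0.05 × 0.95/150) = 0.018, so there is no clear sign of inflation.

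**How firm are the power gains?** Less firm than the variance ratios, because each rests on 150 runs. The approximation Φ(|log OR|/SE − 1.96), applied to the tabled standard errors, gives gains of about 1 point in the two SD 1 rows and at most about 14 points (50%, SD 3: Φ(0.28) = 0.61 to Φ(0.67) = 0.75). The direction and order of size agree with the simulated 1 to 10 points.

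**Does the patient random effect already do this work?** No. Both fits contain it, and the standard error still falls when baseline is added.

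**Limits.** The simulation used a random intercept and four visits, not an unstructured covariance over all visits, and it held within-patient correlation constant over time. Correlation that fades over two years would shrink the gain at late visits.

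**The case against.** The strongest reply is that almost nothing rests on this analysis. The endpoint is exploratory, lies outside the testing hierarchy of SAP 8.4, was not powered, and is reported with nominal p-values (Protocol 12.7.2.3). Under randomization the model without the term is still valid, and its standard error already allows for chance imbalance. All of that stands. It limits the severity but gives no reason to leave the term out.

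SAP 10.4.1 also plans shift tables from baseline for urinalysis parameters, so an imbalance in baseline dipstick blood would be visible by arm. That is true, but the tables are descriptive and adjust nothing in the model.

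The term is not wholly free. If few patients are negative at baseline, it adds a sparse cell to a demanding model and gains little (the 95% row). This stands, and calls for a fallback. SAP 8.7.4 already allows simpler models at the primary analysis when sparsity prevents convergence.

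Adding a covariate to a logistic model can change the odds ratio being estimated. Here the model is already conditional on patient through its random effect, and the mean estimates barely moved (for example −0.82 without and −0.80 with, at 50% and SD 2).

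A reader might infer that every other main model adjusts for its own baseline and that hematuria is the sole exception. The SAP does not support that: the Cox models (8.7.4.1) and the event-rate models (8.7.5) have no such term, nor does the immunosuppressive-use model that shares the hematuria text.

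**Conclusion.** The point holds as a minor, optional improvement. The model omits a relevant baseline covariate that the schedule provides for and the SAP's baseline rule already covers, and neither document explains why.

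The cost is precision. Under the assumed ranges, the variance of the treatment log odds ratio is about 2% to 27% higher-than-needed when expressed as the reduction the term would bring, and simulated power is about 1 to 10 points lower. These figures depend on prevalence and within-patient stability, which the documents do not give; the low end applies if status is weakly correlated over time or nearly everyone is positive at baseline.

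Two stronger readings should be resisted. The omission does not bias the comparison or threaten type I error. Nor can the documents show that baseline hematuria is the strongest predictor, or that it was obtained in every patient: they show that it is scheduled in every patient.

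**What to change.** In SAP 8.7.4 and Protocol 12.7.4, for the hematuria model only, add baseline hematuria (present/absent, chosen by the SAP 6.4.1 rule) as a fixed effect. Word it so that it does not carry over to the immunosuppressive-use model in the same text. Specify it before the unblinding for the analysis in which it will be used, and state that it is dropped only if sparsity prevents convergence.

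The cost is one degree of freedom and a short text change, with no new data.
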